### 8.1.3. Secondary Endpoint

The secondary endpoints of this study are:

#### Groups 1-3 and 5

- Proportion of subjects with  $\geq 1 \log_{10}$  IU/mL decline in HBsAg from Baseline at Week 12
- Proportion of HBeAg-positive subjects who achieve HBeAg loss and seroconversion through 48 weeks of treatment
- Proportion of subjects who achieve HBsAg loss through 48 weeks of treatment
- Proportion of subjects with drug resistance mutations during 48 weeks of treatment
- Change from Baseline in HBV DNA and quantitative HBsAg through 48 weeks of treatment

#### Group 4

- Proportion of subjects experiencing HBV virologic breakthrough (2 consecutive visits of HBV DNA  $\geq 69$  IU/mL) during 12 weeks of GS-9992 treatment
- Proportion of subjects with  $\geq 1 \log_{10}$  IU/mL decline in HBsAg from Baseline at Week 12
- Proportion of HBeAg-positive subjects who achieve HBeAg loss and seroconversion through 48 weeks
- Proportion of subjects who achieve HBsAg loss through 48 weeks
- Change from Baseline in quantitative HBsAg through 48 weeks

## 8.2. Analysis Conventions

### 8.2.1. Analysis Sets

#### 8.2.1.1. Efficacy

The primary analysis set for efficacy analysis is the full analysis set (FAS), defined as all subjects who were randomized to Group 1 or 2, or enrolled in Group 3 or 4 or 5 and who took at least 1 dose of any study drug. Subjects will be analyzed according to the randomized or enrolled treatment assignment.

#### 8.2.1.2. Safety

The primary analysis set for safety analysis is the safety analysis set (SAS), defined as all subjects who took at least 1 dose of any study drug. Subjects will be analyzed according to the treatment actually received.

#### 8.2.1.3. Pharmacokinetics

The pharmacokinetics (PK) analysis set will include all subjects who were randomized to Group 1 or 2, or enrolled in Group 3 or 4 or 5 and took at least 1 dose of any study drug and have at least 1 nonmissing concentration value reported by the PK laboratory.

CCI

#### 8.2.1.4. Biomarkers

The primary analysis set for biomarker analysis is the biomarker analysis set, defined as all subjects who were randomized to Group 1 or 2 or enrolled in Group 3 or 4 or 5 and who took at least 1 dose of any study drug and have at least 1 nonmissing biomarker value for each respective biomarker.

### 8.3. Data Handling Conventions

For the primary efficacy endpoint and the categorical secondary efficacy endpoints, missing data will be handled using a missing = failure approach.

For the drug resistant mutations endpoint, a missing = excluded approach will be employed.

### 8.4. Demographic Data and Baseline Characteristics

Demographic and baseline measurements will be summarized by treatment group and overall using standard descriptive methods.

Demographic summaries will include age, sex, race and ethnicity.

Baseline data will include a summary of body weight, height, body mass index, HBeAg status, HBeAb status, HBsAg ( $\log_{10}$  IU/mL), HBV DNA ( $\log_{10}$  IU/mL), ALT, HBV genotype, previous HBV treatment experience, and additional endpoints as necessary.

## **8.5. Efficacy Analysis**

### **8.5.1. Primary Analysis**

The primary efficacy endpoint, i.e. the proportion of subjects with  $\geq 0.5 \log_{10}$  IU/mL decline in HBsAg from baseline at Week 12, will be evaluated for all groups in the FAS. The 2-sided 95% confidence interval (CI) of the proportion difference (Group 1 – Group 2, Group 3 – Group 2, Group 5 – Group 2) will be constructed by using stratum-adjusted Mantel-Haenszel (MH) proportions, stratified by the randomization stratification factor HBeAg status (positive, negative).

### **8.5.2. Secondary Analyses**

Continuous secondary endpoints will be summarized using conventional descriptive statistics (n, mean, standard deviation, median, Q1, Q3, minimum, and maximum) by treatment group.

Categorical secondary endpoints will be summarized by number and percentage of subjects that meet the endpoint by treatment group.

### **8.5.3. Analysis of Other Endpoints of Interest**

Continuous endpoints will be summarized using conventional descriptive statistics (n, mean, standard deviation, median, Q1, Q3, minimum, and maximum) by treatment group.

Categorical endpoints will be summarized by number and percentage of subjects who meet the endpoint by treatment group.

## **8.6. Safety Analysis**

Safety will be evaluated by assessment of clinical laboratory tests and adverse events. Primary safety analysis will be evaluated through four weeks after last dose of GS-9992.

### **8.6.1. Extent of Exposure**

A subject's extent of exposure to study drug(s) will be generated from the study drug(s) administration data. Exposure data will be summarized by treatment group

### **8.6.2. Adverse Events**

Clinical and laboratory adverse events (AEs) will be coded using the Medical Dictionary for Regulatory Activities (MedDRA). System Organ Class (SOC), High-Level Group Term (HLGT), High-Level Term (HLT), Preferred Term (PT), and Lower-Level Term (LLT) will be attached to the clinical database.

Summaries (number and percentage of subjects) of treatment-emergent (TE) AEs (by SOC and PT) will be provided by treatment group:

- All TEAEs
- TEAEs of Grade 3 or higher
- TEAEs of Grade 2 or higher
- All TE treatment-related AEs
- TE treatment-related AEs of Grade 3 or higher
- TE treatment-related AEs of Grade 2 or higher
- All TE SAEs
- All TE treatment-related SAEs
- All TEAEs leading to premature discontinuation of any study drug
- All TEAEs leading to temporary interruption of any study drug

All AEs collected during the study will be presented in the data listings.

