#### **6.11. Criteria for Discontinuation of Study Treatment**

GS-9992 and/or TAF may be discontinued if the following instances are met:

- A confirmed  $\geq$  Grade 3 AE (excluding isolated ALT elevations) considered related to GS-9992 and/or TAF by the investigator, should discontinue one or both study drug(s)
- A confirmed, clinically significant lab abnormality  $\geq$  Grade 3 (excluding isolated ALT elevations) considered related to GS-9992 and/or TAF by the investigator, should discontinue one or both study drug(s)
- Intercurrent illness that would, in the judgment of the investigator, affect assessments of clinical status to a significant degree
- Unacceptable toxicity or toxicity that, in the judgment of the investigator, compromises the ability to continue study-specific procedures or is considered to not be in the subject's best interest
- HBsAg loss confirmed at least 12 weeks apart
- Subject requests to discontinue for any reason
- Subject noncompliance
- Pregnancy during the study
- Discontinuation of the study at the request of Gilead, a regulatory agency or an institutional review board or independent ethics committee (IRB/IEC)

For Group 5, study treatment(s) will be held in all subjects in the dosing group, if  $\geq 3$  subjects experience a Grade 3 adverse event or  $\geq 2$  subjects experience a Grade 4 or serious adverse event, in the same system organ class (excluding isolated ALT elevations) that is considered related by the investigator(s) to the Graded toxicity. Decisions to reinstate continuation of dosing of study treatment(s) will be made by Gilead Medical Monitor upon review of all safety data generated by subjects dosed to date.

Refer to Section 7.6 for additional discontinuation criteria for Toxicity Management.

HBV will be managed according to local standard of care if subjects are discontinued from the study. Subjects that discontinue all HBV therapy should be followed for 24 weeks or until the initiation of alternative CHB therapy, whichever comes first.

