#### 7.1.6. Summaries of Adverse Events and Deaths

AEs will be summarized based on the Safety Analysis Set.

3 sets of summaries will be generated: (1) all TEAEs for 12 Week Regimen (2) all TEAEs for 48 Week Regimen (Group 1-3, and 5). (3) all AEs during TFFU period (AEs that occur during TFFU after Week 48) will be listed, and summary tables will be presented using the TFFU Analysis Set as appropriate.

A brief, high-level summary of the number and percentage of subjects who experienced at least 1 TEAE in the categories described below will be provided by treatment group. All deaths observed in the study will also be included in this summary.

The number and percentage of subjects who experienced at least 1 TEAE will be provided and summarized by SOC, PT and treatment group:

- TEAEs (with severity)

For the AE categories described below, summaries will be provided by PT and treatment group:

- TEAEs
- TEAEs of Grade 3 or higher
- TE treatment-related AEs
- GS-9992 only TE treatment-related AEs (Group 1, 3-5)
- TE treatment-related AEs of Grade 3 or higher
- TE SAEs
- TE treatment-related SAEs
- TEAEs leading to premature discontinuation of GS-9992
- TEAEs leading to premature discontinuation of TAF
- TEAEs leading to dose modification or temporary interruption of GS-9992
- TEAEs leading to dose modification or temporary interruption of TAF

Multiple events will be counted only once per subject in each summary. Adverse events will be summarized and listed first in alphabetic order by SOC and then by PT in descending order of total frequency within each SOC. For summaries by severity grade, the most severe grade will be used for those AEs that occurred more than once in an individual subject during the study.

In addition to the by-treatment summaries described above, data listings will be provided for the following AEs:

- All AEs, indicating whether the event is treatment-emergent
- All AEs of Grade 3 or higher
- SAEs
- All deaths
- AEs leading to premature discontinuation of any study drug
- AEs leading to dose modification or temporary interruption of any study drug

For subjects in the TFFU Analysis Set, by-subject listings will be provided as follows:

- All AEs
- AEs of Grade 3 or higher
- All SAEs
- All deaths

The listings will indicate whether an event is treatment-emergent, and whether the event occurred during TFFU.

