## **7.7. Changes From Protocol-Specified Safety Analyses**

There are no deviations from the protocol-specified safety analyses.

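### The SAP heads the related, serious and drug-action adverse event tables by preferred term only and omits two Grade 2 or higher tables, yet declares no departure from the protocol's organ-class summaries

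*Protocol*

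**What the plan says.** Protocol 8.6.2 sets one level of detail for all its TEAE tables: "Summaries (number and percentage of subjects) of treatment-emergent (TE) AEs (by SOC and PT) will be provided by treatment group". Ten categories follow: all events, Grade 3 or higher, Grade 2 or higher, the same three restricted to treatment-related events, serious events, related serious events, events leading to premature discontinuation of any study drug, and events leading to temporary interruption of any study drug.

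SAP 7.1.6 uses two headings. The first reads "The number and percentage of subjects who experienced at least 1 TEAE will be provided and summarized by SOC, PT and treatment group" and has one entry, TEAEs with severity. The second reads "For the AE categories described below, summaries will be provided by PT and treatment group" and has eleven entries.

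After both lists the same section adds "Adverse events will be summarized and listed first in alphabetic order by SOC and then by PT in descending order of total frequency", and also "Multiple events will be counted only once per subject in each summary". It further plans a high-level summary, by treatment group, of the number of subjects with at least one TEAE in each category, and by-subject listings.

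SAP 7.7 states: "There are no deviations from the protocol-specified safety analyses".

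**The concern.** Safety and tolerability of the 12-week regimens is a primary objective (Protocol 2). It is assessed descriptively across groups of about 10 to 30 subjects. In groups of that size, related or serious events within one organ class can be spread over several preferred terms and appear as a run of single-subject rows. SOC rows let a reader see how many subjects were affected in that class. The protocol promised them for every TEAE table.

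If the SAP is programmed as headed, that level disappears for the tables restricted by relatedness, seriousness or action taken with study drug, and two tables disappear altogether. A reader of SAP 7.7 would be told that nothing had changed. The SAP also gives the programmer two instructions, a PT heading and an SOC-then-PT ordering, which do not describe the same table.

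**Working it through.** No sample size, power or alpha figure bears on this point. The check is a comparison of the two lists, followed by a bound on what PT counts can tell.

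**Step 1. Compare the lists (Protocol 8.6.2 against SAP 7.1.6).**

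| Protocol summary, all by SOC and PT | In SAP 7.1.6 |
|---|---|
| All TEAEs | SOC and PT, with severity; also repeated under the PT heading |
| Grade 3 or higher | PT heading |
| Grade 2 or higher | not listed |
| Related | PT heading |
| Related, Grade 3 or higher | PT heading |
| Related, Grade 2 or higher | not listed |
| Serious | PT heading |
| Related serious | PT heading |
| Discontinuation | PT heading, split into GS-9992 and TAF |
| Interruption | PT heading, split by drug and widened to dose modification |

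Of the ten, 1 keeps SOC, 7 move to PT and 2 are absent: 1 + 7 + 2 = 10. The SAP's eleven PT entries are reconciled as follows. Five of the seven take one line each and two take two lines each (5 + 4 = 9). The repeat of all TEAEs and a new table of events related to GS-9992 only make 11.

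**Step 2. What the severity table recovers.** It shows each subject's worst grade by SOC, regardless of cause. All-cause Grade 3 or higher and Grade 2 or higher can therefore be read by SOC. Relatedness, seriousness and drug action cannot. That leaves six protocol summaries headed without SOC and not recoverable from the severity table (related; related Grade 3 or higher; serious; related serious; discontinuation; interruption), plus related Grade 2 or higher, which has no table.

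**Step 3. Can PT rows be added to an SOC count?** Let c1, ..., ck be the subject counts for the PTs in one SOC, and n the group size (30 planned in Group 5). Each subject counts once per row but may appear in several rows, so

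max(ci) ≤ SOC count ≤ min(c1 + ... + ck, n).

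- PT counts 1, 1, 1: SOC count 1 to 3
- PT counts 2, 1: SOC count 2 to 3
- PT counts 2, 2, 1: SOC count 2 to 5
- PT counts 1, 1: SOC count 1 to 2

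The PT rows alone do not fix the SOC count in any of these.

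**Step 4. Add the high-level summary.** It gives the total number of subjects in a category, T. The upper bound becomes min(c1 + ... + ck, T, n). The lower bound becomes the larger of max(ci) and T minus the sum of the PT counts in all other SOCs.

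- If the only rows are 1, 1, 1 in one SOC and T = 3, the lower bound is 3 − 0 = 3 and the count is exactly 3.
- If a second SOC also has rows 1 and 1 and T = 3, the lower bound for the first SOC is max(1, 3 − 2) = 1 and the upper bound is 3. The range is again 1 to 3.

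The high-level table therefore settles simple cases, but not those where events fall in more than one organ class.

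**Step 5. Compare with the declaration.** Steps 1 and 2 show departures from Protocol 8.6.2. SAP 7.7 lists none. SAP 6.4, by contrast, does record the dropped pharmacokinetic analysis.

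**The case against.** The strongest reply is that the SAP may not mean what its heading says. The ordering sentence, "Adverse events will be summarized and listed first in alphabetic order by SOC and then by PT in descending order of total frequency", follows all the category lists, names no particular table and covers summaries as well as listings. It fits tables with an SOC structure better than PT-only tables. This stands in part: it makes the SAP ambiguous, so one cannot say flatly that SOC counts will be absent. But it fixes an order and does not promise SOC subject counts. All TEAEs also appear under both headings, which serves a purpose only if the second heading yields a different table.

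A second reply is that little is lost. The high-level summary, the all-cause severity table, and the listings of all, Grade 3 or higher and serious events together bound the missing counts or allow them to be derived. SOC is also held in the AE dataset (SAP 7.1.1). This stands, and it limits the point to presentation.

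A reader might infer something stronger. The Group 5 hold in Protocol 6.11 counts subjects with events "in the same system organ class (excluding isolated ALT elevations) that is considered related by the investigator(s) to the Graded toxicity", and it could seem that PT-only tables leave that rule without its data. The documents do not support this. The rule operates during the trial, and the Medical Monitor decides on resuming dosing after reviewing all safety data to date. The first planned analysis (SAP 2.1) waits for cleaned Group 5 data through Week 12, the end of the 12-week GS-9992 course. Restoring SOC would not produce the hold-rule count either: a related Grade 3 or higher table pools Grades 3 and 4, which the rule treats separately, and does not set aside isolated ALT elevations.

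**Conclusion.** The point holds as a documentation and reporting defect of small size. SAP 7.1.6 is inconsistent with Protocol 8.6.2 and with its own ordering sentence, and the no-deviation statement in SAP 7.7 is incorrect as written. Seven of ten protocol summaries are headed without SOC and two are omitted. For six of the seven, the SOC subject count cannot be read from the severity table or obtained by adding PT rows.

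No data are lost, no efficacy estimate changes, and no in-trial safety decision depends on these tables. It would also go too far to say that a cluster of events in one organ class would be hidden: the all-cause SOC table with severity is planned by treatment group, and the documents do not say how often related events spread over several PTs. What is missing is a direct view of related, serious and drug-action events by organ class, which the protocol specified for a primary safety objective.

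The conclusion rests on two assumptions: that the SAP headings govern table content, and that the severity table is by grade. SAP 7.1.2 also mentions a mild, moderate and severe scale, but the reference to severity grade in 7.1.6 favours the former.

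**What to change.** In SAP 7.1.6, reword the second heading so that it names SOC as well as PT and treatment group. Do this for all its categories or, at minimum, for the related, related Grade 3 or higher, serious and related serious tables. This also reconciles the heading with the ordering sentence. If some tables are meant to stay at PT level, limit the ordering sentence to the tables it covers.

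Then correct SAP 7.7. Either restore the two Grade 2 or higher summaries, or list their omission with a reason, together with any other departure that remains, such as tables kept at PT level.

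SOC is already coded, so no new data are needed. The cost is a few lines of SAP text and slightly longer tables.

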### **8.6.3. Laboratory Evaluations**

Selected laboratory data (using conventional units) will be summarized using only observed data. Data and change from baseline at all scheduled time points will be summarized.

Graded laboratory abnormalities will be defined using the grading scheme in [Appendix 3](#).

Incidence of treatment-emergent laboratory abnormalities will be summarized. All laboratory abnormalities will be included in the listings of laboratory data.

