**Table 1-7. GS-US-320-0108 and GS-US-320-0110: Treatment-Emergent Grade 3 or 4 Laboratory Abnormalities Reported for at Least 1% of Subjects in Either Treatment Group in the Overall TAF Phase 3 Safety Population (Safety Analysis Set)**

	TAF 25 mg (N = 866)	TDF 300 mg (N = 432)
Maximum Postbaseline Toxicity Grade (N)	859	428
Grade 3	225 (26.2%)	96 (22.4%)
Grade 4	44 (5.1%)	30 (7.0%)
Chemistry		
Alanine Aminotransferase (N)	859	428
Grade 3	52 (6.1%)	27 (6.3%)
Grade 4	18 (2.1%)	13 (3.0%)
Amylase (N)	859	427
Grade 3	22 (2.6%)	9 (2.1%)
Aspartate Aminotransferase (N)	859	428
Grade 3	25 (2.9%)	18 (4.2%)
Grade 4	3 (0.3%)	5 (1.2%)
Creatine Kinase (N)	859	428
Grade 3	16 (1.9%)	7 (1.6%)
Grade 4	9 (1.0%)	6 (1.4%)
Fasting Glucose (Hyperglycemia) (N)	857	425
Grade 3	9 (1.1%)	0
Fasting LDL Cholesterol (N)	837	417
Grade 3	37 (4.4%)	1 (0.2%)
Nonfasting Glucose (Hyperglycemia) (N)	856	426
Grade 3	25 (2.9%)	7 (1.6%)
Urinalysis		
Occult Blood (N)	859	426
Grade 3	66 (7.7%)	30 (7.0%)
Urine Erythrocytes (N)	768	386
Grade 3	59 (7.7%)	35 (9.1%)
Urine Glucose (N)	859	426
Grade 3	41 (4.8%)	5 (1.2%)

Denominator for percentage (N) is the number of subjects in the safety analysis set with at least 1 postbaseline laboratory value for the test.

Subjects were counted once for the maximum postbaseline severity for each laboratory test. For urinalysis (i.e., urine glucose, urine protein, and urine RBC), the highest grade is Grade 3.

For nonfasting glucose, the maximum postbaseline toxicity grades, instead of treatment-emergent abnormalities, were summarized, because nonfasting glucose test was not done at baseline.

'Hyper' means high and 'Hypo' means low.

Source: TAF Week 48 ISS, Table 20

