##### **6.8.5.1. Blood Sampling**

Blood samples will be collected for the following laboratory analyses:

- Hematology:
  - Hematocrit, hemoglobin, platelet count, red blood cell (RBC) count, white blood cell (WBC) count with differential (absolute and percentage), including lymphocytes, monocytes, neutrophils, eosinophils, basophils, and mean corpuscular volume (MCV), and
- Coagulation panel
  - Prothrombin time, partial thromboplastin time [PTT] and international normalized ratio [INR])

- Chemistry:
  - Alkaline phosphatase, AST, ALT, total bilirubin, direct and indirect bilirubin, total cholesterol, high-density lipoprotein (HDL), low-density lipoprotein (LDL), triglycerides, total protein, albumin, lactic acid dehydrogenase (LDH), creatine kinase (CK), bicarbonate, blood urea nitrogen (BUN), calcium, chloride, creatinine (see below), glucose, phosphorus, magnesium, potassium, sodium, uric acid, and lipase (reflex amylase testing is performed in subjects with total lipase  $>1.5 \times$  upper limit of normal [ULN])
- Serum pregnancy test (females of childbearing potential only)
- Follicle-stimulating hormone (FSH) testing (For female subjects post-menopausal for less than two years, if FSH  $< 40$  mIU/ mL a serum pregnancy test will be required)

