Hypouricemia Adult and Pediatric ≥ 1 year	1.5 mg/dL to < LLN 87 μmol/L to < LLN N/A	1.0 to < 1.5 mg/dL 57 to < 87 μmol/L 1.0 mg/dl to <LLN- 57 μmol to <LLN	0.5 to < 1.0 mg/dL 27 to < 57 μmol/L 0.5 to < 1.0 mg/dL 27 to < 57 μmol/L	< 0.5 mg/dL < 27 μmol/L < 0.5 mg/dL < 27 μmol/L
Creatinine**	> 1.50 to 2.00 mg/dL > 133 to 177 μmol/L	> 2.00 to 3.00 mg/dL > 177 to 265 μmol/L	> 3.00 to 6.00 mg/dL > 265 to 530 μmol/L	> 6.00 mg/dL > 530 μmol/L
Bicarbonate Adult and Pediatric ≥ 4 Years	16.0 mEq/L to < LLN 16.0 mmol/L to < LLN	11.0 to < 16.0 mEq/L 11.0 to < 16.0 mmol/L	8.0 to < 11.0 mEq/L 8.0 to < 11.0 mmol/L	< 8.0 mEq/L < 8.0 mmol/L
Pediatric < 4 Years	NA	11.0 mEq/L to <LLN 11.0 mmol/L to <LLN	8.0 to < 11.0 mEq/L 8.0 to < 11.0 mmol/L	< 8.0 mEq/L < 8.0 mmol/L

CHEMISTRY				
	Grade 1	Grade 2	Grade 3	Grade 4
Triglycerides (Fasting)	NA	500 to 750 mg/dL 5.64–8.47 mmol/L	> 750 to 1200 mg/dL > 8.47–13.55 mmol/L	> 1200 mg/dL > 13.55 mmol/L
LDL (Fasting) Adult	130 to 160 mg/dL 3.35 to 4.15 mmol/L	>160 to 190 mg/dL >4.15 to 4.92 mmol/L	> 190 mg/dL >4.92 mmol/L	NA
LDL (Fasting) Pediatric >2 to <18 years	110 to 130 mg/dL 2.84 to 3.37 mmol/L	>130 to 190 mg/dL >3.37 to 4.92 mmol/L	> 190 mg/dL >4.92 mmol/L	NA
Hypercholesterolemia (Fasting)	200 to 239 mg/dL 5.16 to 6.19 mmol/L	> 239 to 300 mg/dL > 6.19 to 7.77 mmol/L	> 300 mg/dL > 7.77 mmol/L	NA
Pediatric < 18 Years	170 to 199 mg/dL 4.39 to 5.15 mmol/L	> 199 to 300 mg/dL > 5.15 to 7.77 mmol/L	> 300 mg/dL > 7.77 mmol/L	NA
Creatine Kinase	3.0 to < 6.0 × ULN	6.0 to < 10.0 × ULN	10.0 to < 20.0 × ULN	≥ 20.0 × ULN

\* Calcium should be corrected for albumin if albumin is < 4.0 g/dL

\*\* An overlap between the Grade 1 scale and the Lab's normal range for creatinine may result for Male subjects >70 yrs. Please follow the Gilead convention of grading any result within the LLN and ULN a 0.

ENZYMES				
	Grade 1	Grade 2	Grade 3	Grade 4
AST (SGOT)	1.25 to 2.50 × ULN	> 2.50 to 5.00 × ULN	> 5.00 to 10.00 × ULN	> 10.00 × ULN
ALT (SGPT)	1.25 to 2.50 × ULN	> 2.50 to 5.00 × ULN	> 5.00 to 10.00 × ULN	> 10.00 × ULN
GGT	1.25 to 2.50 × ULN	> 2.50 to 5.00 × ULN	> 5.00 to 10.00 × ULN	> 10.00 × ULN
Alkaline Phosphatase	1.25 to 2.50 × ULN	> 2.50 to 5.00 × ULN	> 5.00 to 10.00 × ULN	> 10.00 × ULN
Total Amylase	> 1.0 to 1.5 × ULN	> 1.5 to 2.0 × ULN	> 2.0 to 5.0 × ULN	> 5.0 × ULN
Pancreatic Amylase	> 1.0 to 1.5 × ULN	> 1.5 to 2.0 × ULN	> 2.0 to 5.0 × ULN	> 5.0 × ULN

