### **3.6. Missing Data and Outliers**

#### **3.6.1. Missing Data**

In general, missing data will not be imputed unless methods for handling missing data are specified. Exceptions are presented in this document.

A missing baseline laboratory result will be treated as normal (ie, no toxicity grade) for the laboratory abnormality summary.

Both the baseline and post-baseline borderline results for HBeAg, hepatitis B e antibody (HBeAb), HBsAg, and hepatitis B surface antibody (HBsAb) will be imputed following the rules below:

- HBsAb/HBeAb borderline → HBsAb/HBeAb negative
- HBsAg/HBeAg borderline → HBsAg/HBeAg positive

For missing last dose date of study drug, imputation rules are described in Section 3.8.1. The handling of missing or incomplete dates for adverse event (AE) onset is described in Section 7.1.5.2, and for prior and concomitant medications in Section 7.4.

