#### For the **Analysis for 48 Week Regimen**:

- For subjects treated with GS-9992 and TAF (ie, Group 1, 3 and 5):

3 days after permanent discontinuation of TAF or 30 days after permanent discontinuation of GS-9992, whichever comes last

- For subjects treated with TAF only (ie, Group 2):

3 days after permanent discontinuation of TAF

- Subjects treated with GS-9992 and commercially available NUC(s) (ie, Group 4) are not included in treatment-emergent **Analysis for 48 Week Regimen**.

If the relevant baseline laboratory value is missing, any abnormality of at least Grade 1 observed within the time frame specified above will be considered treatment-emergent.

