### 7.2.3.3. Summaries of Laboratory Abnormalities

Laboratory data that are categorical will be summarized using the number and percentage of subjects in the study with the given response at baseline and each scheduled postbaseline visit for treatment emergent laboratory abnormalities. Laboratory abnormalities during TFFU period will be summarized using the number and percentage of subjects in the study with the given response at TFFU baseline and each scheduled post treatment visit.

3 sets of summaries will be generated: (1) all TE laboratory abnormalities for 12 Week Regimen (2) all TE laboratory abnormalities for 48 Week Regimen for Groups 1-3, 5. (3) all laboratory abnormalities during TFFU after Week 48 for subjects in the TFFU Analysis Set will be listed, and summary tables will be presented using the TFFU Analysis Set as appropriate.

The following summaries (number and percentage of subjects) for laboratory abnormalities will be provided by lab test and by treatment group; subjects will be categorized according to the most severe postbaseline or post TFFU baseline abnormality grade for a given lab test:

- Graded laboratory abnormalities
- Grade 3 or 4 laboratory abnormalities

For all summaries of laboratory abnormalities, the denominator is the number of subjects with nonmissing postbaseline or post TFFU baseline values. A by-subject listing of Grade 3 or 4 laboratory abnormalities, and all graded laboratory abnormalities will be provided by subject ID number and visit in chronological order. This listing will include all test results that were collected throughout the study for the lab test of interest, with all applicable severity grades or abnormal flags displayed.

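### Reflex-only amylase would be tabulated as a treatment-emergent incidence, although its denominator is limited to subjects with raised lipase and its baseline is usually missing by design

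*Protocol*

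**What the plan says.** **Collection.** Protocol 6.8.5.1 puts lipase in the routine chemistry panel. Amylase is not in the panel: "reflex amylase testing is performed in subjects with total lipase" above 1.5 x ULN.

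**Grading.** The enzyme table in Protocol Appendix 3 has a row for "Total Amylase", graded from above 1.0 x ULN. In the same table the reflex trigger corresponds to lipase Grade 2 or higher.

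**Summary.** Protocol 8.6.3 states: "Incidence of treatment-emergent laboratory abnormalities will be summarized". SAP 7.2.3.3 tabulates graded abnormalities test by test and group by group, and "the denominator is the number of subjects with nonmissing postbaseline or post TFFU baseline values".

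**Missing baseline.** SAP 3.6.1: "A missing baseline laboratory result will be treated as normal (ie, no toxicity grade) for the laboratory abnormality summary". SAP 7.2.3.1 adds that in this case "any abnormality of at least Grade 1 observed within the time frame specified above will be considered treatment-emergent".

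The SAP makes no exception for reflex tests and does not name amylase. It reaches the graded tables because it has a grading row and the tables run over laboratory tests.

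**The concern.** Each rule is ordinary for a test done in everyone at every visit. Applied to a reflex test, they do two things.

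1. The denominator becomes the subjects already selected for raised lipase. The table would print the chance of raised amylase given raised lipase under a heading that reads as incidence in the treatment group.
2. Baseline amylase is absent by design in anyone whose lipase did not trigger the reflex before dosing. Any elevation seen later is then called treatment-emergent, including one that was present all along.

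Safety and tolerability is the first-listed primary objective, and the groups are small: about 10 in Group 2, about 20 in Group 4 and about 30 each in Groups 1, 3 and 5. An amylase percentage could differ between groups mainly because different numbers of subjects happened to be reflexed, and a reader could take that for a pancreatic signal.

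**Working it through.** The documents state no expected amylase incidence and no reflex rate, so there is no planned figure to reproduce.

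**1. The sponsor's own earlier table.** Protocol Table 1-7 (TAF Phase 3) uses the same kind of per-test denominator. Grade 3 amylase is 22/859 = 2.6% and 9/427 = 2.1%, as printed. The amylase denominators (859 and 427) match or nearly match those for ALT (859 and 428), so almost everyone had an amylase result and the convention did no harm. Here it would.

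**2. Same events, two denominators.** Let f be the share of subjects with at least one post-baseline reflex amylase.

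SAP percentage / percentage over all treated = (n/tested) / (n/treated) = treated/tested = 1/f.

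| Assumed f | 1/f | Expected tested of 30 | Expected tested of 10 |
|---|---|---|---|
| 5% | 20 | 1.5 | 0.5 |
| 10% | 10 | 3 | 1 |
| 20% | 5 | 6 | 2 |

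Illustration at f = 10%: in a group of 30, 3 are tested. If 2 are elevated, the SAP rule prints 2/3 = 66.7%, against 2/30 = 6.7% over all treated. In Group 2, 1 of 10 is tested, so the printed rate can only be 0% or 100%.

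**3. Against testing everyone.** The all-treated percentage is not the true incidence, because raised amylase with lipase at or below 1.5 x ULN is never observed. Let s be the share of elevations that the reflex catches. Then

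SAP percentage / percentage under universal testing = s/f.

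| Assumed f | s = 1 | s = 0.5 |
|---|---|---|
| 5% | 20 | 10 |
| 10% | 10 | 5 |
| 20% | 5 | 2.5 |
| 30% | 3.3 | 1.7 |
| 50% | 2.0 | 1.0 |

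When few subjects are reflexed, s may be well below 0.5. A simulation of correlated lipase and amylase shows this. Its assumptions were 2 pre-dose and 9 post-baseline visits, within-subject correlation 0.5 to 0.8, lipase-amylase correlation 0.4 to 0.7, and per-visit probabilities of 1% to 8% for the lipase trigger and 3% to 10% for raised amylase. The factor was 1.1 to 5.9 against universal testing, and 3 to 27 against all treated. In one scenario f = 6.2%, the SAP rule gave 20.8% and universal testing gave 13.3%: a ratio of 20.8/13.3 = 1.6.

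**4. The treatment-emergent label.** Take a subject with a steady Grade 2 amylase, lipase at or below 1.5 x ULN before dosing and above it once afterwards. Baseline amylase is missing, so it is set to normal, and the later value counts as treatment-emergent Grade 2 although nothing changed. Had lipase triggered the reflex on Day 1, the same subject would have a Grade 2 baseline and no treatment-emergent event. In the simulation, 62% to 92% of subjects with an observed elevation were classed as treatment-emergent. Of those so classed, 4% to 49% already had raised amylase at baseline.

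**5. Precedent.** A footnote to Table 1-7 reads: "For nonfasting glucose, the maximum postbaseline toxicity grades, instead of treatment-emergent abnormalities, were summarized, because nonfasting glucose test was not done at baseline". The SAP makes no corresponding exception.

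**The case against.** Several points on the other side are sound.

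- **Size.** A reader might infer that the amylase incidence is inflated several-fold as a matter of fact. The documents do not support that: neither f nor s is given, and against universal testing the factor can be close to 1.
- **Label.** A reader might also infer that nearly every elevated amylase would be called treatment-emergent. SAP 3.8.3 takes the last nonmissing value on or before first dose as baseline, and the eligibility criteria do not exclude raised lipase. Subjects reflexed at screening or Day 1 therefore have a baseline and must rise by a grade under SAP 7.2.3.1.
- **Denominator.** SAP 7.2.3.3 does not literally say that the nonmissing value must be for the test in question. Because the summaries are made test by test, that is the natural reading, but it is a reading.
- **Precedent.** Nonfasting glucose in Table 1-7 was not done at baseline at all, whereas amylase is done pre-dose when the reflex fires. The parallel holds only for subjects without a pre-dose amylase.
- **Consequence.** SAP 7.2 plans no inferential statistics for laboratory data. Every reflexed subject already has lipase of Grade 2 or higher in a table with a near-complete denominator; SAP 7.2.1 plots lipase; and SAP 7.2.3.3 lists graded results by subject. A careful reader could recover the denominator from the count and percentage.

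These points limit the size of the problem. They do not remove the mismatch between the label and the quantity printed. The sentence in Protocol 8.6.3 is sound in itself; the SAP rules fail to deliver it for this analyte.

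**Conclusion.** The concern holds in a limited form. Followed as written, the SAP prints the rate of raised amylase among subjects with lipase above 1.5 x ULN. Where there is no pre-dose amylase, it labels any elevation treatment-emergent.

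Relative to the same events over all treated subjects the percentage is larger by exactly 1/f: 20-fold to 5-fold if f is 5% to 20%, which is an assumption. Relative to universal testing the factor is s/f. The bias is upward whenever lipase and amylase are positively related, but it may be less than 2-fold. It would also be wrong to take the all-treated percentage, such as 2/30, as the true incidence: it is a lower bound.

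The effect is confined to one descriptive safety analyte. The primary efficacy endpoint is untouched.

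**What to change.** In SAP 7.2.3.1 and 7.2.3.3:

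1. Exempt reflex-only tests from the rule that a missing baseline counts as normal.
2. Where there is no pre-dose amylase, show maximum post-baseline grade, or list the results only, without the treatment-emergent label.
3. Present amylase as n over the number reflex-tested, with the number treated beside it, and label it as conditional on lipase above 1.5 x ULN.
4. Use treatment-emergent lipase, which is measured in all subjects, as the group-level pancreatic incidence.

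Do not count unreflexed subjects as normal unless the result is labelled a lower bound. That would fill in results for an unmeasured analyte, and Protocol 8.6.3 restricts the summaries of selected laboratory data to observed values.

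The cost is one SAP exception and one programming exception. If the SAP is already final, its Section 1 requires the change to be documented in the clinical study report. No extra sampling is needed.
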